8.0 Reporting Requirements

8.1 Expected Adverse Events and Grading

The Investigator or physician designee is responsible for verifying and providing source documentation for all adverse events and assigning the attribution for each event for all subjects enrolled on the trial

The research team will ensure that all adverse events are entered into the study case report form CORe/PDMS. All adverse events entered into the case report form must have a verifiable source document that is maintained in the subject's medical record. PDMS/CORe will be used as the electronic case report form for this protocol.

1. All patients will be registered in CORe
2. The severity of the adverse events (AEs) will be graded according to the Common Terminology Criteria v4.0 (CTCAE)
3. For the purpose of causality:
 - a. Known adverse events of lenalidomide and ipilimumab will be reported as **definitely** related.
 - b. When the relationship of the adverse event cannot be ruled out with certainty the AE may be considered **probable or possible related**.
 - c. Adverse events known to be related to drugs used for supportive treatment will be scored as **unrelated**.
 - d. The principal investigator will be final arbiter in determining causality assessment.

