7.0 Statistical Considerations

Overview

The primary objective of this study will be to assess the safety of lenalidomide alternating with ipilimumab in stem cell transplantation. Patients will receive lenalidomide alternating with ipilimumab for 8 cycles (lenalidomide for 21 days, then one dose of ipilimumab, then repeat lenalidomide 4 weeks later, etc.). The starting and highest allowable dose of lenalidomide in this study will be 10 mg/d. Dose reductions to 5 mg may be allowed within patient based on clinical practice. Ipilimumab is fixed at 3 mg/kg. If the starting combination of lenalidomide 10 mg/d and ipilimumab 3 mg/kg results in toxicity, as defined below in the toxicity monitoring rule, in the first 3 of 3 patients, subsequent patients will be started at a lower combination dose of lenalidomide 5 mg/d and ipilimumab 3 mg/kg.

Secondary objectives include assessing overall response rate, overall survival, progression-free survival, and the cumulative incidence of acute and chronic GVHD with the competing risk of relapse in allogeneic transplant patients.

Safety Monitoring

We expect to accrue a total of 40 transplant patients onto two arms: Autologous (N=25) and allogeneic (N=15). All patients will receive lenalidomide alternating with ipilimumab (L+I). Each transplant arm will be monitored separately using monitoring rules for toxicity. The following stopping rules and boundaries were developed using the Multc Lean Desktop application (version 2.1.0) in the Biostatistics department.

The Principal Investigator and assigned Research Nurse will review the enrolled patients monthly while on active treatment to assess adverse events and stopping rules. The Biostatistician will be consulted as necessary. The data monitoring plan will be provided by the MD Anderson IND Office. This office is responsible to monitor the protocol conduct and data entry.

Toxicity monitoring rules: Each transplant arm (either autologous or allogeneic) will be monitored separately for toxicity. If there is a high probability of observing more than a 30% toxicity rate in either arm, that arm will be stopped. Toxicity for this stopping rule will include the following, at any time during active study treatment, which is defined as the first eight cycles plus 30 days following the last dose of study drug:

- Any grade 4 hematological toxicity at least probably related to study drug that does not resolve within 2 weeks

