- Any immune-mediated reaction to ipilimumab that requires permanent cessation of the drug

- Any other grade 3-5 organ toxicity at least probably related to study drug
- (Allogeneic arm only) Any acute grade III or higher GVHD.

Bayesian sequential monitoring⁷ will be employed to perform interim safety monitoring targeting a toxicity rate of not more than 30%. Patients will be monitored in cohorts of 1.

Autologous Arm

For the autologous arm, accrual will be stopped early if

$$\Pr [\text{prob(toxicity)} > 0.30 \mid \text{data}] > 0.975$$

That is, if we determine that there is a greater than 97.5% chance that the toxicity rate is greater than 30% in this arm, then accrual will be stopped. We assume a beta (0.6, 1.4) prior distribution for the toxicity rate, which has a mean of 0.3 corresponding to the 30% target toxicity rate. Stopping boundaries corresponding to this probability criterion are to terminate accrual in autologous patients if

If there are this many (or more) patients in the autologous transplant arm with Toxicity	Stop the arm if this many patients in the arm
3	3
4	4-5
5	5-7
6	6-9
7	7-11
8	8-13
9	9-16
10	10-18
11	11-21
12	12-23
13	13-24
14	ALWAYS STOP

Patients must complete at least two cycles of treatment or have toxicity to be included in the rule. Patients who complete at least two cycles but drop out without experiencing toxicity will be included but not counted as toxicities. If accrual onto this arm is stopped, the study will continue enrolling patients to the allogeneic transplant arm.

The rule will reset at lenalidomide 5 mg if the first 3 of 3 patients at the combination 10 mg lenalidomide dose experience toxicity. If the rule resets after the first three patients, we will continue to enroll up to 25 patients in the autologous arm at the lower combination dose using lenalidomide 5 mg. The Biostatistical collaborator will be consulted as necessary.

The operating characteristics of this rule are shown below.

Table 1. Operating Characteristics for Toxicity Stopping Rule in Autologous Arm

If the true toxicity rate is...	Early Stopping Probability	Achieved Sample Size Percentiles		
		25th	50th	75th
0.1	0.0014	25	25	25
0.2	0.0163	25	25	25
0.3	0.0891	25	25	25
0.4	0.3013	18	25	25
0.5	0.6324	7	16	25
0.6	0.8929	5	9	16
0.7	0.9872	3	5	9

Allogeneic Arm

For the allogeneic arm, accrual will be stopped early if

$$\Pr [\text{prob(toxicity)} > 0.30 \mid \text{data}] > 0.95$$

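### Section 8.1 has two mandatory attribution rules that can give one event opposite labels, and the label decides whether it counts in two of the four toxicity components

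*Combined protocol and SAP*

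**What the plan says.** Section 8.1 makes the investigator or physician designee responsible for attributing each event, then lists four causality items.

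- **3a:** "Known adverse events of lenalidomide and ipilimumab will be reported as" definitely related.
- **3b:** "When the relationship of the adverse event cannot be ruled out with certainty the AE may be considered" probable or possible.
- **3c:** "Adverse events known to be related to drugs used for supportive treatment will be scored as" unrelated.
- **3d:** "The principal investigator will be final arbiter in determining causality assessment".

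Section 7.0 defines toxicity for the stopping rule by four components. Two use the relatedness label:

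- "Any grade 4 hematological toxicity at least probably related to study drug that does not resolve within 2 weeks"
- "Any other grade 3-5 organ toxicity at least probably related to study drug"

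Two do not use it directly:

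- "Any immune-mediated reaction to ipilimumab that requires permanent cessation of the drug"
- "Any acute grade III or higher GVHD" (allogeneic arm only)

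Toxicity so defined drives the separate stopping rule in each arm and the reset to a lower lenalidomide starting dose if the first 3 of 3 patients have toxicity. The primary analysis is the toxicity rate in each arm with a 95% credible interval.

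**The concern.** Items 3a and 3c are both written as mandatory, and neither asks about timing, alternative cause or course after the drug is stopped. Where a known study-drug event is also known for a supportive drug, one item puts it above the relatedness threshold and the other below. Nothing says which prevails.

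A second problem needs no overlap. As written, 3a passes every known study-drug event through the relatedness filter, even when transplant, underlying disease or infection is the evident cause. That conflicts with the per-event attribution at the start of the same section. All patients receive the combination, so there is no untreated group against which background events could be judged. Attribution is the only filter.

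Applying 3a can count background events as drug toxicity and stop an arm unnecessarily. Applying 3c can remove real drug toxicity and let an arm continue.

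**Working it through.** **1. Can one event meet both items?** Section 4.3 (item 6, on anticoagulation) says lenalidomide raises thrombotic risk and that combining it with steroids raises the risk further. Section 4.1 uses steroids to manage ipilimumab toxicity. A grade 3 thrombosis in a patient on such steroids is therefore a known lenalidomide event and arguably one known for a supportive drug. A narrower reading of 3c, limited to events shown in that patient to come from a supportive drug, makes the overlap rarer but does not remove it: 3a still calls the same event definitely related if it is a known study-drug event.

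**2. Where does the label act?** It acts only on patients whose sole qualifying event falls in the grade 4 hematological or the other grade 3-5 organ component. A patient who already counts through GVHD or ipilimumab cessation counts whatever the label.

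**3. Reproduce the plan's operating characteristics.** Inputs from Section 7.0: beta(0.6, 1.4) prior; threshold 0.30; cut-offs 0.975 (autologous, N=25) and 0.95 (allogeneic, N=15); cohorts of 1. After x toxicities in n patients, stop if Pr(θ > 0.30) > cut-off, where θ ~ beta(0.6 + x, 1.4 + n − x). I used an exact binomial recursion and counted no stop at the last patient.

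| True rate | Table 1 | Recomputed | Table 2 | Recomputed (0.95 criterion) |
|---|---|---|---|---|
| 0.2 | 0.0163 | 0.0163 | 0.0210 | 0.0210 |
| 0.3 | 0.0891 | 0.0891 | 0.0998 | 0.0998 |
| 0.4 | 0.3013 | 0.3014 | 0.2780 | 0.2780 |
| 0.5 | 0.6324 | 0.6324 | 0.5367 | 0.5367 |

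The printed allogeneic boundaries do not match the 0.95 criterion. At 3 of 4 the posterior probability is 0.935, yet the table says stop. Allogeneic results are therefore given both ways below. As in Tables 1 and 2, 3 of 3 counts as a stop, although the text resets the rule there.

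**4. Background events counted through 3a.** Assumed, since the documents give no rates: drug-caused rate t = 0.25; independent background rate b of listed, otherwise qualifying events from 0.05 to 0.20; every one counted. Counted rate = 1 − (1 − t)(1 − b).

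- b = 0.05: 1 − 0.75 × 0.95 = 0.2875
- b = 0.20: 1 − 0.75 × 0.80 = 0.40

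| Counted rate | Autologous stop | Allogeneic, 0.95 criterion | Allogeneic, printed boundaries |
|---|---|---|---|
| 0.25 (b = 0) | 0.040 | 0.050 | 0.094 |
| 0.2875 | 0.074 | 0.085 | 0.147 |
| 0.40 | 0.301 | 0.278 | 0.385 |

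The chance that the first 3 of 3 patients have toxicity moves from 0.25³ = 0.016 to 0.40³ = 0.064.

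**5. Toxicities removed through 3c.** Assume a true rate of 0.40 with a quarter relabelled unrelated. The counted rate is 0.40 × 0.75 = 0.30, and autologous stopping falls from 0.301 to 0.089. With half relabelled, the counted rate is 0.20 and stopping is 0.016.

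**6. Shared events alone.** Assume 20% of patients have unambiguous toxicity and a further 10%, 20% or 30% have only a shared event. If shared events are labelled unrelated, autologous stopping is 0.016. If they are labelled definitely related, it is 0.089, 0.301 or 0.632. The allogeneic figures under the 0.95 criterion are 0.021 against 0.100, 0.278 or 0.537.

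**7. Effect on the primary estimate.** Assume the credible interval uses the monitoring prior and the patient stays evaluable. The posterior mean is (0.6 + x)/(2 + n), so each relabelled patient moves it by 1/27 = 0.037 (autologous) or 1/17 = 0.059 (allogeneic).

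**The case against.** Item 3d makes the principal investigator final arbiter, so one label is recorded. A reader might infer that a shared event both counts and does not count, or that the primary endpoint is undefined. The documents do not support that: the rate is defined, but it rests on a choice for which no criterion is written.

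A reader might also infer that attribution is purely mechanical. It is not. The opening of Section 8.1 calls for attribution of each event, 3b allows for uncertainty, and Section 4.1 asks for other causes to be excluded in colitis and hepatitis. This softens the point but does not answer it, because 3a and 3c as worded leave no room for the result of that assessment. Item 3b does not help either, since its probable-or-possible label spans the at-least-probable threshold.

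The scope is also limited: two of the four components do not use the label.

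Finally, the rates used above are not in the documents. The full lists of known events are in the package inserts (Appendices E and F), which were not available for this review. The thrombosis text describes raised risk in combination, so it illustrates an overlap without showing how often it occurs. Step 4 is a worst case within its assumptions, because it counts every background event and gives 3d no role. At its lower end, autologous stopping moves only from 0.040 to 0.074. All of this stands as a limit on size, not on the textual conflict.

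**Conclusion.** The conflict is real and should be corrected. Items 3a and 3c can require opposite labels for one event, with no precedence and no criteria for the arbiter. Item 3a taken literally also overrides case-level attribution. The recorded label decides whether an event counts in two of the four toxicity components, and through them it affects the stopping rule in each arm, the 3-of-3 reset and the primary toxicity rate.

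The documents do not show how large the effect is or in which direction it runs. The calculations show only that stopping behaviour is sensitive to the label if affected events are common. A reader might take them as an estimate of bias in this trial, but no event frequencies are given that would support that.

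**What to change.** Replace 3a and 3c with one case-level attribution rule on a single ordered scale, judged on timing, alternative causes and course after the drug is stopped. State that an event known for a study drug is not automatically definitely related, and that one also known for a supportive drug is not automatically unrelated. Split the probable-or-possible label in 3b so that the scale shows clearly where the at-least-probable threshold falls. Keep the principal investigator as final arbiter under 3d, applying these criteria.

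Add a sensitivity estimate of the toxicity rate in each arm that counts all events meeting the type and grade criteria of Section 7.0, regardless of attribution. The planned summary by arm, type and grade does not provide this patient-level rate.

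The cost is a wording change, slightly more judgment per event and one extra analysis. Sample size, prior and stopping criteria do not change.

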8.2 Adverse events considered serious

1. Graft Failure/rejection.
2. Any expected or unexpected event resulting in an irreversible condition and/or leading to death.

8.3 Serious Adverse Event Reporting (SAE)

An adverse event or suspected adverse reaction is considered "serious" if, in the view of either the investigator or the sponsor, it results in any of the following outcomes:

- Death
- A life-threatening adverse drug experience – any adverse experience that places the patient, in the view of the initial reporter, at immediate risk of death from the adverse experience as it occurred. It does not include an adverse

experience that, had it occurred in a more severe form, might have caused death.

- Inpatient hospitalization or prolongation of existing hospitalization
- A persistent or significant incapacity or substantial disruption of the ability to conduct normal life functions.
- A congenital anomaly/birth defect.

Important medical events that may not result in death, be life-threatening, or require hospitalization may be considered a serious adverse drug experience when, based upon appropriate medical judgment, they may jeopardize the patient or subject and may require medical or surgical intervention to prevent one of the outcomes listed in this definition. Examples of such medical events include allergic bronchospasm requiring intensive treatment in an emergency room or at home, blood dyscrasias or convulsions that do not result in inpatient hospitalization, or the development of drug dependency or drug abuse (21 CFR 312.32).

- Important medical events as defined above, may also be considered serious adverse events. Any important medical event can and should be reported as an SAE if deemed appropriate by the Principal Investigator or the IND Sponsor, IND Office.
- All events occurring during the conduct of a protocol and meeting the definition of a SAE must be reported to the IRB in accordance with the timeframes and procedures outlined in "The University of Texas M. D. Anderson Cancer Center Institutional Review Board Policy for Investigators on Reporting Unanticipated Adverse Events for Drugs and Devices". Unless stated otherwise in the protocol, all SAEs, expected or unexpected, must be reported to the IND Office, regardless of attribution (within 5 working days of knowledge of the event).
- **All life-threatening or fatal events**, that are unexpected, and related to the study drug, must have a written report submitted within **24 hours** (next working day) of knowledge of the event to the Safety Project Manager in the IND Office.
- **Unless otherwise noted, the electronic SAE application (eSAE) will be utilized for safety reporting to the IND Office and MDACC IRB.**
- **Serious adverse events will be captured from the time of the first protocol-specific intervention, until 30 days after the last dose of drug, unless the participant withdraws consent. Serious adverse events must be followed until clinical recovery is complete and laboratory tests have returned to baseline, progression of the event has stabilized, or there has been acceptable resolution of the event.**
- **Additionally, any serious adverse events that occur after the 30 day time period that are related to the study treatment must be reported to the IND Office. This may include the development of a secondary malignancy.**

Reporting to FDA:

- Serious adverse events will be forwarded to FDA by the IND Sponsor (Safety Project Manager IND Office) according to 21 CFR 312.32.

It is the responsibility of the PI and the research team to ensure serious adverse events are reported according to the Code of Federal Regulations, Good Clinical Practices, the protocol guidelines, the sponsor's guidelines, and Institutional Review Board policy.

9.0 Criteria for Removal from the Study

- 9.1** Completion of study. This is defined as three years after the last dose of Ipilimumab.
- 9.2** Disease progression.
- 9.3** Intolerable side effects.
- 9.4** Unable to follow study directions.
- 9.5** Withdrawal of consent.

